2. BACKGROUND AND OBJECTIVES

The management of fractures of the medial epicondyle is a controversial issue in paediatric fracture care [3]. These fractures typically occur in children around 10-12 years old [4], with or without dislocation of the elbow joint. The debate for clinicians is whether to realign and hold the bone fragments with operative fixation, or whether to allow the fragments to heal in their current position without surgery by resting the elbow in a cast.

Observational studies have demonstrated support for both operative and non-operative treatment strategies, generating uncertainty amongst surgeons. Two published systematic reviews have demonstrated disagreement in the management of this injury [4, 5]. One systematic review concluded that nonsurgical treatment offers excellent functional results equivalent to surgical treatment [5]. The other concludes that surgical fixation should be strongly considered to achieve union of the bone fragments thereby maximising elbow stability for an increasingly athletic child population [4]. To add further to the debate, a widely used 'evidence-based review' textbook has recently advocated against surgery, citing increased long-term pain and stiffness compared to non-operative treatment [6].

Much of the controversy has arisen because there have been no prospective studies evaluating the treatment of these fractures. Current literature has serious methodological limitations, especially with regard to inconsistent follow-up, no standardisation to treatment approaches, infrequent use of patient reported outcomes, and selection bias for operative fixation [6]. There has also been a lack of agreement on how to record successful outcomes; with radiographic union of the fracture fragments being the most commonly used outcome, and pain or function being infrequently recorded, although there is known to be poor correlation between radiographic union and functional outcomes [5]. The uncertainty within the literature has resulted in considerable variation in clinical practice. There is an increasing tendency toward surgery, which has been particularly driven by US literature identifying the athletic demands of children and adolescents, and the expectations of early mobilisation and return to sport [3-7].

An audit of surgical practice amongst 30 centres in the UK was conducted and identified 520 medial epicondyle fractures over a 3-year period. Overall, 225 (43%) of these fractures were treated with surgical fixation, with the remaining 295 (57%) treated non-operatively. 39 children (8%) had an incarcerated fragment, which is an absolute requirement for surgery. The decision to offer 'operative intervention' is highly dependent upon the surgeon. Surgical fixation is thought to improve the likelihood of 'bony union' of the fracture. However, this is balanced against the small but definite risks from the surgery including infection, nerve damage around the elbow, broken and retained metalwork, and the risks associated with general anaesthesia. It is unclear whether bony union has any bearing on functional recovery, including return to sports.

There is a clear and pressing need to inform patients about the benefits or otherwise of operative fixation versus non-operative treatment, and the need to inform commissioners regarding the costs of the different treatment strategies to the NHS and society. The SCIENCE study is a randomised superiority trial of operative fixation versus non-operative treatment for medial epicondyle fractures of the humerus in children [8, 9].

The aim of this pragmatic randomised controlled superiority trial is to evaluate the clinical and costeffectiveness of operative fixation versus non-operative treatment for displaced medial epicondyle fractures of the elbow in children.

The estimand for the primary objective (including the analysis of the primary outcome) is described in Table 1.

Table 1: Estimand-to-analysis table

Primary Objective: To quantify and draw inferences on observed differences in function for children between operative fixation versus non-operative fixation at 1-year post-randomisation for fractures of the medial epicondyle in children

Estimand: A single primary estimand will be the difference in the levels of physical function in children aged 7 to15 years old between those treated with operative and non-operative fixation, 1 year following an injury no more two weeks old, leading to an uncomplicated displaced medial epicondyle fracture of the humerus, irrespective of fixation technique used and any unforeseen technical difficulties making the delivery of either randomised intervention impossible or difficult and/or receiving any other interventions that are part of the standard of care.

| Treatment: Operative fixation vs non-operativ | e treatment |
|---|--|
| Estimand | Analysis |
| Target population | Analysis set |
| Children aged between 7 and 15 years who present at participating UK hospitals with a medial epicondyle fracture of the humerus. | All randomised participants. |
| Variable | Outcome measure |
| Physical Function measured on the child reported PROMIS Upper Extremity scale at 1-year post-randomisation. | Continuous outcome bounded scale (PROMIS Upper Extremity T-score) where higher scores indicate better function better function, at 12 months post-randomisation |
| Handling of intercurrent events | Handling of missing data |
| Switching Treatment arm: Participants who receive a different intervention to that which they were allocated will be analysed according to their randomised allocation Further surgery: Participants that require additional surgical intervention on their elbows are also considered part of the treatment All intercurrent events will be handled under a treatment-policy strategy ¹ . | Multilevel modelling of outcome scores over time, imputes implicitly intermittent missing data over the post- randomisation period of follow-up. The underlying assumption is missing at random (MAR) conditional on all other outcome scores and minimisation factors. This is the main approach to handling missing data. Sensitivity analysis : The MAR assumption can be strengthened by conditioning on additional baseline covariates predictive of the outcome and missingness. Missing data arising from participants discontinuing in the study prior to 12 months under a NMAR (Not Missing at random) informative missing data mechanism will be explored under two approaches: a) the extended Hausman-Wise-Diggle-Kenward selection model when drop out depends on outcome scores prior to drop out and where this is jointly modelled with the longitudinal outcome. b) using controlled multiple imputation: δ - based imputation (see section (Details in Section 6.3: Missing data) where the primary analysis model is augmented with an offset term with values set to the fixed values of the missing and repeated over |

a range (+/- 1 SD PROMIS score). This is done to assess the impact of drop-out on inferences

| Population-level summary measure | Analysis approach |
|---|---|
| Average Treatment effect (ATE): Mean difference in physical function scores at 12 months, between the two randomised arms, as randomised, measured on the PROMIS Upper extremity scale. | Analysis of repeated measures of PROMIS Upper Extremity scores over time including all randomised participants as randomised and including all measurement occasions (at baseline, and all follow-up times up to 12 months) using multilevel linear random effects model. |
| | Sensitivity analyses: Primary estimand (ITT) for the average treatment effect (ATE) using regression adjustment for the propensity of allocated treatment received and including the quantiles of the propensity score distribution as a covariate. |

¹Strategies defined in E9 (R1) include treatment policy, while on treatment, principal stratum and hypothetical [1, 10]

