3. STUDY METHODS

3.1 Trial Design/framework

SCIENCE is a multi-centre, prospective, randomised, superiority trial using a two-arm parallel group design in at least 35 centres across the UK, New Zealand and Australia. Children aged 7-15 years presenting for treatment for displaced medial epicondyle fracture of the elbow, will be randomised in a 1:1 ratio to either receive operative fixation, or non-operative treatment. The nature of the treatment means that neither the patients and their parents/guardians, nor the treating clinician can be blinded to the treatment received; however, the treating clinical team will take no part in the follow-up assessments and outcome assessors will be blinded to the participant's treatment allocation.

The trial includes an internal pilot (phase 1) which was designed to confirm the expected rate of recruitment in a large-scale, multi-centre randomised controlled trial. This pilot was planned to take place at 20 centres over 12 months. The Data Safety and Monitoring Committee (DSMC) was tasked to make a recommendation to the Trial Steering Committee (TSC) regarding trial continuation in the event that the recruitment target for the internal pilot is not met. Otherwise, the trial would continue into the main phase (phase 2), and patients from the internal pilot would be included in the final analysis. The main trial phase was planned to be recruiting from a minimum of 35 centres treating children's fractures across the UK, stratified by centre to account for centre specific effects, and by dislocation status of the elbow. Follow-up was planned to be made electronically (sent by e-mail or text message) for the Patient Reported Outcomes at 6 weeks, 3 months, 6 months and 12 months (Primary outcome time-point).

All children aged 7-15 years old presenting at the trial centres with a displaced medial epicondyle fracture of the humerus are potentially eligible to take part in the trial. After consent has been gained, a local research associate will collect baseline demographic data, the Patient Reported Outcomes Measurement Information System (PROMIS) Upper Extremity Score for Children Computer Adaptive Test, DASH S/PA Module, Wong Baker Faces Pain Score, and health-related quality of life using the EuroQoL EQ-5DY.

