3.3 Sample Size

Extremity Score for Children. Raw scores are translated into standardised T scores with a population mean of 50 and a Standard Deviation (SD) of 10. The 'Minimally Clinically Important Difference' (MCID) for the PROMIS Upper Extremity Score amongst children with milder forms of disability has been demonstrated to be three to

four [11], we seek to find a difference of four points. Assuming a SD of 10, a total of 266 patients (133 in each arm) is required to provide 90% power at the 5% level (two-sided) to detect a 4-point difference between the groups. Allowing for a conservative 20% loss to follow-up, we plan to recruit 334 patients in total for this trial (167 per arm).

The SD of 10 derived by PROMIS was based on a sample of children with a higher proportion of chronic illness than the general population [12], and it is anticipated that the variation in outcomes in the treatment of acute medial epicondyle fractures is likely to be less than in a chronic illness.

Independent verification of the sample size is available in

Z:\CSM_SCIENCE\Statistical Analysis\4. Sample Size**SCIENCE_SampleSize_Verification_04Apr2019.docx**, stored in the confidential statistical section of the TMF.

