6.2 Analysis Methods

Analysis of Primary estimand (ATE): A Treatment Policy Analysis

Unadjusted summary statistics of the PROMIS scores will be displayed by treatment allocation using means and standard deviations. A multivariate linear mixed-effects regression model using repeated measures (level 1) nested within participants (level 2) will then be used to compare the treatment groups including all available data on randomised participants, at all-time points up to and including 12 months [28]. The model will include fixed effects to adjust for the minimisation factor used by the randomisation system: initial elbow dislocation status, and fixed effects for age and gender. A treatment by time interaction (as a categorical variable) will be included. The random part of the model will include random intercept terms for centres (level 3) and the individual participant (level 2) to account for the dependence of observations of participants within the same centre and observations within the same participant over time. At the individual participant level, it will also include a random coefficient for the effect of time (measurement occasion) and an unstructured covariance structure for the association between the random intercept and occasion as shown in the equations below describing the functional relationship between the outcome indexed by centre, individual participant and measurement occasions:

$$Y_{c,i,t} = \alpha_{c,i} + \beta_i Time_i + \theta Treatment_i + \gamma Treatment_i Time_i + \delta_k Covariate_{k,i} + \varepsilon_{i,t}$$

where c index centres, i individual participants and t measurement occasion (e.g. baseline, 1^{st} , 2^{nd} and 3^{rd} follow-up visit) and $Time_i$ is a variable representing the time elapsed between randomisation and PROMIS questionnaire completed.

 θ denotes the overall treatment effect and γ the interaction of treatment by time and covariates will be the stratification factors used in the randomisation protocol.

Note: Care needs to be taken to code observation occasions appropriately. Ideally, the exact timing of outcome measurement relative to the timing of randomisation will be used and if observation timings are highly unbalanced over time, time covariates will be centred around the mean time for fitting.

The random part of the model, partitions the variance to centre-level, individual participant and observation level and completes the model specification as follows:

Centre-level random effects

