$$\alpha_{c,i} = \alpha_0 + u_{a,c} + u_{\alpha,i}$$

where $u_{a,c} \sim Normal(0, \sigma_{centre}^2)$ quantifying between centre variation in baseline means and α_0 denoting the overall baseline mean

Individual participant-level random effects:

$$\beta_i = \beta_0 + u_{\beta,i}$$

$$\begin{pmatrix} u_{\alpha,i} \\ u_{\beta,i} \end{pmatrix} = MVN\begin{pmatrix} \sigma_{\alpha}^2 & \sigma_{\alpha,\beta} \\ \sigma_{\alpha,\beta} & \sigma_{\beta}^2 \end{pmatrix}$$

MVN denotes a multivariate normal distribution quantifying the between-individual variation in means and linear change over time, respectively along with their correlation and $\varepsilon_{i,t} \sim Normal(0, \sigma_{i,t}^2)$ the residual observational level variance.

This will be compared with a model assuming independence between the random intercept and slope with respect to reductions in the likelihood function and the precision of the estimate for the random slope.

Non-linearity for the effect terms will also be considered using restricted cubic splines in the fixed part of the model. Even when highly non-linear patterns are evident, the limited number of measurement occasions— only five, including the baseline—restricts the complexity needed for an adequate fit. This means that we will need at most 2-3 knots, which should be positioned at the centiles of the time axis distribution [29] and choosing the model with the smallest deviance and the simplest functional form for the effect of time in the fixed part of the model, will be used after considering a maximum of three models: (a) linear (b) cubic spline with 2 knots (c) cubic spline 3 knots.

Sites with less than 5 participants will be grouped together to allow reliable estimation [30, 31].

The adjusted mean differences (treatment effect) will be presented, along with 95% confidence intervals and p-values.

As a supporting analysis to check model assumptions, a simple analysis of covariance (ANCOVA) of the primary outcome at 12 months will also be presented, adjusting only for the baseline PROMIS score, following protocol analysis specifications.

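### The primary mixed model does not adjust the 12-month PROMIS contrast for baseline PROMIS, so some available precision is given up; the size depends on an unstated correlation and is probably small.

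*SAP*

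**What the plan says.** SAP Section 2, Table 1, describes the primary analysis as a repeated-measures model "including all measurement occasions (at baseline, and all follow-up times up to 12 months) using multilevel linear random effects model". Section 6.2 confirms that baseline is one of the outcome occasions, counting "only five, including the baseline".

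The Section 6.2 equation has a treatment main effect (theta), a treatment-by-time interaction (gamma), random intercepts for centre and child, and a random slope for time within child. No sentence requires the arms to share a mean at baseline. The overall baseline mean that is mentioned there defines only the intercept.

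On covariates, "The model will include fixed effects to adjust for the minimisation factor used by the randomisation system: initial elbow dislocation status", with age and gender added. The note under the equation lists only the stratification factors. Baseline PROMIS is in neither list. Protocol Section 10.1 likewise adjusts the mixed model for the stratification factors only.

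Baseline PROMIS is a covariate in one place, the 12-month ANCOVA, which is run "adjusting only for the baseline PROMIS score, following protocol analysis specifications". SAP Sections 3.7 and 6.2 label that analysis secondary or supporting.

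**The concern.** Having the baseline score in the outcome vector can look like adjusting for it. When the arm means are free at baseline, it is not. With a separate mean for each arm at each visit and no missing data, the model's 12-month contrast is the difference in 12-month means, apart from the other covariates.

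The baseline score is collected on every child before randomisation, when the true arm difference is zero. SAP Section 6.3 itself counts it among the prognostic factors to be examined for drop-out. Minimisation covers centre and dislocation status only, so baseline PROMIS is balanced only by chance. Two things follow: precision that the data could supply is not used, and a chance baseline difference moves the primary estimate. No planned 12-month PROMIS analysis is specified to adjust for both baseline PROMIS and dislocation status.

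Section 6.2 also calls theta the overall treatment effect and never says which combination of theta and gamma is the 12-month effect. If time zero is randomisation, theta is the arm difference at baseline.

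**Working it through.** **Inputs from SAP Sections 3.1 and 3.3.** Allocation is 1:1. The assumed SD is 10 and the target difference is 4 points, with 90% power and a two-sided 5% test. The evaluable number is 266 (133 per arm). With 20% loss, recruitment is 334 (167 per arm).

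**Input not in the documents.** Rho, the correlation between baseline and 12-month PROMIS, is assumed to be 0.1 to 0.5. Protocol Section 2 says that baseline questions are asked just after the fracture is found, so low values are plausible.

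**Step 1. The plan's own figure.** The normal approximation gives 132 per arm. With the t distribution, power is 89.9% at 132 per arm and 90.1% at 133, so 133 per arm (266) reproduces. Then 133/0.8 = 166.25, rounded up to 167 per arm, or 334. Baseline adjustment plays no part in this.

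**Step 2. Unadjusted contrast.** SE = 10 × √(2/133) = 1.226. Normal-approximation power = Φ(4/1.226 − 1.96) = 90.4%. Generalised least squares over 0, 1.5, 3, 6 and 12 months, with categorical time, complete data and arms free at baseline, gave 1.226 at every rho tried. Baseline therefore contributes nothing in that case.

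**Step 3. Contrast adjusted for baseline.** Variance is multiplied by (1 − rho²), so SE = 1.226 × √(1 − rho²). The last column is the shift in the unadjusted estimate from a chance baseline difference of 1.96 SE, that is rho × 1.96 × 1.226 (2.4 points × rho), if the baseline SD is also 10.

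| rho (assumed) | variance saved | SE | power at 133 per arm | shift (points) |
|---|---|---|---|---|
| 0 | 0% | 1.226 | 90.4% | 0 |
| 0.1 | 1% | 1.220 | 90.6% | 0.24 |
| 0.2 | 4% | 1.202 | 91.5% | 0.48 |
| 0.3 | 9% | 1.170 | 92.8% | 0.72 |
| 0.5 | 25% | 1.062 | 96.5% | 1.20 |

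A simulation of 4,000 trials compared the raw 12-month difference with ANCOVA. At rho 0.2, 0.4 and 0.6 the raw estimate moved with the baseline difference at slopes of 0.18, 0.42 and 0.59. The ANCOVA slope was about 0 throughout.

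**Step 4. Missing data.** With 334 recruited, 20% monotone drop-out and an assumed correlation of 0.5 between follow-up visits, a common baseline mean with the correct covariance lowers the SE from 1.190 to 1.170 (rho 0.2) and from 1.188 to 1.142 (rho 0.3).

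**Step 5. Does the remedy depend on the covariance?** The SAP's random intercept and slope were fitted to assumed true covariances (SD 10 at every visit, categorical visits, complete data, 133 per arm), and the arms were then constrained to a common baseline mean. The true SE of the 12-month contrast, against 1.226 without the constraint, is:

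| rho | follow-up correlation 0.5 | follow-up correlation 0.7 |
|---|---|---|
| 0 | 1.309 | 1.402 |
| 0.1 | 1.277 | 1.358 |
| 0.2 | 1.236 | 1.304 |
| 0.3 | 1.186 | 1.240 |

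At low rho the constraint makes matters worse. With rho 0 and follow-up correlation 0.7, the SE that the constrained model reports is 1.285 against a true 1.402, so its intervals would be too narrow. The random-slope structure implies a dependence of the 12-month score on baseline that the data may not have.

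**The case against.** The strongest defence is that nothing here is invalid. Over repeated randomisations the unadjusted contrast is unbiased. The planned 266 reproduces without baseline adjustment. The model already adjusts for dislocation status, age and gender, and the protocol prescribes both the mixed model and the baseline-only ANCOVA. All of that stands.

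It is also fair that the lack of adjustment is exact only with categorical time and complete data. Section 6.2 describes time as categorical in one sentence and as elapsed time in another, and allows linear and spline forms. With linear time the unconstrained SE is 1.179 rather than 1.226 (rho 0.2, follow-up correlation 0.5). With missing follow-up, baseline scores enter through the likelihood. Neither replaces adjustment: in both settings a common baseline mean with the correct covariance still lowers the SE (to 1.086 and 1.170 at rho 0.2).

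The supporting ANCOVA would show a discrepancy but could not explain it. It also differs from the primary model in centre effects, dislocation status, age, gender and the handling of missing data.

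A reader might infer that deleting theta is a costless repair. Step 5 shows that it is not under the SAP's covariance. Section 6.2 also allows time to be centred at its mean, and theta would then not be the baseline difference at all.

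**Conclusion.** The point holds as one of efficiency and clarity. As written, the primary model leaves the 12-month contrast unadjusted for a baseline score that the trial already collects (exactly so with categorical time and complete data), and the estimate moves with a chance baseline difference at a slope of about rho when the two SDs are equal.

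The saving is 1% to 9% of variance for rho of 0.1 to 0.3, which takes power at 133 per arm from 90.4% to between 90.6% and 92.8%. The 25% saving needs rho of 0.5, which nothing in the documents supports. At rho of 0 nothing is gained. These figures assume SD 10 and complete data at 133 per arm.

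A reader might infer that the primary result is biased or the trial underpowered. The documents do not support either: allocation is randomised, and the sample size was derived without baseline adjustment. The change is worth making because it costs almost nothing and also settles which contrast is the 12-month effect.

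**What to change.** In SAP Table 1 and Section 6.2, take as outcomes only the scores at 6 weeks and 3, 6 and 12 months. Fit categorical visit, treatment-by-visit, baseline PROMIS and baseline-by-visit as fixed effects, and keep the existing covariates and centre effects. Name the treatment contrast at the 12-month visit as the primary effect.

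An alternative is to keep baseline as an outcome with a common arm mean, but only with categorical visits and an unstructured covariance across visits.

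Add dislocation status to the supporting ANCOVA, and report this next to the baseline-only version that the protocol specifies.

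The cost is SAP wording, with a note of the departure from the mixed model in Protocol Section 10.1, made before any unblinded analysis. No new data are needed. The model spends a few degrees of freedom, and a child with a missing baseline score needs the covariate imputation already planned in SAP Section 6.3. Under the covariate version, a child with no follow-up score contributes nothing to the fit, and the SAP should say so beside its all-randomised analysis set.
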